Table 1: Schedule of Assessments	15
Table 2: Summary of Lorundrostat and Matching Placebo Characteristics	35
Table 3: Clinical Laboratory Analytes.....	71

LIST OF FIGURES

Figure 1 Study Flow.....	14
--------------------------	----

Endpoints:

Primary Endpoint:

- Placebo-adjusted change from baseline in automated office blood pressure (AOBP) SBP at Study Week 4

[REDACTED]

■

[REDACTED]

■

[REDACTED]

■

[REDACTED]

■

[REDACTED]

■

[REDACTED]

■

[REDACTED]

[REDACTED]

■

[REDACTED]

■

[REDACTED]

[REDACTED]

■

[REDACTED]

Safety Endpoints:

- Incidence and severity of adverse events (AEs)
- Clinically significant changes in vital signs (body temperature, heart rate, and respiratory rate), physical examination and electrocardiogram (ECG) parameters
- Clinically significant changes in clinical laboratory assessments (hematology, chemistry, and urinalysis)
- Incidence of AEs of Special Interest (AESI)
 - Modification of study drug dose due to hyperkalemia (e.g., dose reduction, dose hold, or permanent dose discontinuation)
 - Modification of study drug dose due to hyponatremia (e.g., dose reduction, dose hold, or permanent dose discontinuation)
 - Hypotension with symptoms (e.g., light-headedness, dizziness, presyncope, or syncope)
 - Severely elevated blood pressure (BP; AOBP SBP >180 mmHg or AOBP DBP >110 mmHg)
 - Modification of study drug dose due to hypercortisolism (morning serum cortisol >35 µg/dL, confirmed by 24-hour urinary free cortisol)
 - Discontinuation of study drug due to hypocortisolism confirmed by adrenocorticotrophic hormone (ACTH; Cosyntropin) stimulation test
 - Overdose of study drug
 - Modification of study drug dose due to reduction in kidney function (e.g., dose reduction, dose hold, or permanent dose discontinuation)

[REDACTED]

■

[REDACTED]

Methodology:

This is a randomized, double-blind (DB), placebo controlled, crossover study with a two-period, two-sequence (2x2) design evaluating the efficacy and safety of 25 mg QD lorundrostat (an aldosterone synthase inhibitor [ASI]) in addition to a SGLT2i for the treatment of hypertension in subjects with CKD and albuminuria despite receiving stable treatment with an ACEi or an ARB. Subjects will be at least 18 years old with hypertension, and mild to severe CKD with albuminuria at the Screening Visit. The study consists of a 2-week screening period, a 2-week run-in period where subjects will either begin study provided dapagliflozin 10 mg or continue on their regularly prescribed SGLT2i, and two DB 4-week treatment periods separated by a 4-week washout period (Figure 1). Subjects will be randomized (1:1) to two treatment sequences: lorundrostat-placebo (LP) and placebo-lorundrostat (PL).

Treatment allocation will be organized as follows:

- Treatment Period 1 (DB Study Week 0 to Study Week 4): Subjects will receive a lorundrostat 25 mg (sequence LP) or one matching lorundrostat-placebo tablet (sequence PL) dosed orally QD.
- Washout (Study Week 4 to Study Week 8): All subjects will receive matching placebo dosed orally QD.
- Treatment Period 2 (DB Study Week 0 to Study Week 4): Subjects will receive one matching lorundrostat-placebo tablet (sequence LP) or a lorundrostat 25 mg (sequence PL) dosed orally QD.

During the DB and Washout periods, subjects will continue their background therapy including ACEi/ARB and SGLT2i.

Following the completion of the study, subjects will be offered the opportunity to participate in a separate open label extension (OLE) study. If subjects do not enter the OLE, a final End-of-Study (EoS) safety visit will take place 2 weeks after the last dose of study drug.

Number of Subjects (planned): Approximately 60 subjects

Eligibility Criteria:

Subjects not meeting all inclusion criteria, or meeting at least one exclusion criterion, may be re-screened if there is a reasonable probability of reversal. Retesting of laboratory samples, and a repeat AOBP assessment is allowed in the event of technical failure. Inclusion in the study of any subject who meets all eligibility criteria on rescreening will be at the discretion of the Investigator.

Inclusion Criteria:

Subjects eligible for inclusion in this study must meet **all** the following criteria:

1. Written informed consent, obtained before any study-related assessment is performed
2. At least 18 years of age at the time of signing the informed consent form (ICF)
3. At Screening, UACR of 200-5000 mg/g, inclusive, in first morning urine void
4. At Screening, eGFR of ≥ 30 mL/min/1.73 m²
5. At Screening, AOBP SBP of 135-180 mmHg, inclusive
6. At Randomization, AOBP SBP of 135-180 mmHg, inclusive
7. On a stable treatment with an ACEi or ARB for at least 4 weeks prior to Screening
8. At Screening, serum cortisol (morning measurement, blood draw as close to 8 AM as possible between 3 and 22 µg/dL, inclusive)
9. At Screening, body mass index (BMI) of ≥ 18 kg/m²

10. Fertile male subjects and female subjects of childbearing potential must agree to use an acceptable method of contraception from the Screening Visit to 28 days after the last dose of study drug in each study part
11. Willing and able to comply with the study instructions and attend all scheduled study visits, and are capable of providing informed consent

Exclusion criteria:

Subjects meeting any of the following criteria are **not** eligible for inclusion in this study:

1. Women who are pregnant, plan to become pregnant, or are breast-feeding
2. Subjects with known hypersensitivity to lorundrostat or any of its respective excipients
3. Subjects with known hypersensitivity to dapagliflozin or any of its respective excipients (subjects beginning dapagliflozin only)
4. Treatment, or anticipated treatment, with any prohibited medication within the timeframes described in [Section 6.9](#) of this protocol.
5. Treatment, or anticipated treatment, with triamterene and amiloride
6. Participation in a trial involving an investigational device or drug within 4 weeks or 5 half-lives (whichever is longer) prior to the Screening Visit
7. Previous treatment with lorundrostat or other ASI within 4 weeks or 5 half-lives (whichever is longer) prior to the Screening Visit
8. At Screening, serum potassium >5.0 mmol/L
9. At Randomization, serum potassium >5.0 mmol/L (prior to first dosing of study drug)
10. At Screening, serum sodium <135 mmol/L (corrected for hyperglycemia using the Katz formula). Rescreening of subjects with an exclusionary serum sodium is only allowed if two consecutive measurements at least one week apart are ≥ 135 mmol/L
11. Total bilirubin >2x upper limit of normal (ULN) except for those with a diagnosis of Gilbert's syndrome, unless approved by the Medical Monitor
12. History of clinically significant hyponatremia within 1 year prior to Screening
13. History of adrenal insufficiency or an abnormal ACTH stimulation test within 1 year prior to Screening
14. Hospitalization for the treatment of urgent or emergent hypertension within 1 year prior to Screening
15. Current, known or presumed white coat hypertension/significant white coat effect (as defined in the study reference manual [SRM])
16. Current, known or presumed orthostatic hypotension
17. Current, known or presumed autonomic dysfunction
18. Arm circumference >55 centimeters at Screening
19. Subjects with a previously proven secondary cause of hypertension are excluded with the following exceptions:
 - a. Subjects with documented sleep apnea are eligible to participate
 - b. Subjects with documented primary hyperaldosteronism are eligible to participate if they discontinue use of a mineralocorticoid receptor antagonist (MRA). They should have <20 mmHg increase in AOBP SBP, and AOBP SBP <150 mmHg at Randomization. MRA treatment may be tapered over a one-week period.

20. Use of epithelial sodium channel (ENaC) inhibitors or MRAs, including, but not limited to amiloride, triamterene, spironolactone, eplerenone, finerenone, from 4 weeks prior to the Screening Visit and during study participation. With the exception of MRAs in primary aldosteronism.
21. Medical history of kidney disease related to autoimmune diseases (lupus, anti-neutrophil cytoplasmic antibody [ANCA] vasculitis), multiple myeloma or other known paraproteins, infiltrative diseases of the kidney, obstructive nephropathy, cystic kidney diseases, and renal transplantation
22. Medical history of advanced liver disease, including cirrhosis
23. Medical history of active autoimmune disease or recent (within 30 days) or anticipated need for immunosuppressive therapy
24. Subjects with a medical history of urosepsis and pyelonephritis, lower limb amputation, genital mycotic infections, necrotizing fasciitis of the perineum (Fournier's Gangrene)
25. History of heart failure, myocardial infarction, stroke, or transient ischemic attack within 6 months prior to Screening. Heart failure of New York Heart Association (NYHA) Class II or more requires approval by the Medical Monitor
26. Diabetes mellitus with a glycosylated hemoglobin (HbA_{1c}) >10% (>86 mmol/mol) at Screening
27. Diabetes mellitus with >1 severe hypoglycemic event or severe diabetic ketoacidosis event (events requiring external help) in the 12 months prior to Screening, or with a history of impaired hypoglycemia awareness at Screening
28. Planned major surgery requiring hospitalization during the study period or performed within 4 weeks prior to the Screening Visit
29. History of malignant neoplasms within the 5 years prior to Screening except for known history of basal and squamous cell skin cancer and any carcinoma *in-situ*
30. Known or suspected abuse of illicit drugs or alcohol within 1 year prior to the Screening Visit
31. In the opinion of the Principal Investigator (PI), any other condition that will preclude participation in the study

Test Products, Dosage, and Mode of Administration:

Lorundrostat will be provided in 12.5 mg, and 25 mg tablets (equivalent to 14.74 mg, and 29.48 mg of lorundrostat monohydrobormide [HBr]). The daily dose of lorundrostat will not exceed 25 mg.

Lorundrostat: 25 mg tablets taken orally QD at approximately the same time each morning for 4 weeks.

Reference Product, Dosage and Mode of Administration:

Lorundrostat-placebo: Tablet matching the appearance of lorundrostat but without active substance, administered analogously to lorundrostat.

Duration of Subject's Participation Including Follow-up:

The expected duration of the study for each subject from Screening to the End of Study visit is expected to be:
Approximately 18 weeks

Statistical Methods:

Analysis Sets

The intent-to-treat (ITT) analysis set includes all subjects, regardless of whether treatment was received.

The full analysis set (FAS) will include all subjects who receive at least one dose of study drug. Subjects will be categorized according to the treatment assignment.

The safety analysis set (SAF) will include all subjects who receive at least one dose of study drug. Subjects will be categorized according to the treatment received in the respective study periods.

The population pharmacokinetics (popPK) analysis set will include all subjects who received at least one dose of lorundrostat and had at least one evaluable popPK sample taken. Subjects in this analysis set will be categorized according to the treatment received.

Sample Size

Approximately 60 subjects randomized in a 1:1 ratio to the two sequences (LP and PL) will provide 85% power to detect a placebo-adjusted change in AOBP SBP of at least 5.5 mmHg, assuming a 14 mmHg as a standard deviation of change, and 1-sided alpha of 0.05.

Statistical Analyses

Unless otherwise specified, demographic and baseline characteristics will be summarized for the ITT analysis set. Efficacy outcomes will be analyzed using the FAS, unless otherwise specified. Safety outcome analyses will be performed on the SAF.

[figure not shown]
For continuous variables, the descriptive statistics of n, mean, standard deviation, median, 25th percentile, 75th percentile, minimum, and maximum will be summarized. The frequency and percentage of observed levels will be reported for all categorical variables.

The primary analysis of the primary efficacy estimand will assess the superiority of lorundrostat treatment compared to placebo in change from baseline in AOBP SBP at Study Week 4. Each subject contributes two pairs of treatment observations (change at Study Week 4 from Study Week 0 and, change at Study Week 12 from Study Week 8). A mixed model for repeated measures (MMRM) including treatment arm (Lorundrostat and Placebo), sequence (LP and PL) and Treatment Period (Period 1 and Period 2) as fixed effects, subject (sequence), as random (repeated) effect, and baseline (Study Week 0 and Study Week 8) AOBP SBP as a covariate will be used in the analysis. An estimate of the least square means, and the associated standard errors and 90% confidence intervals (CIs) of change from baseline at Study Week 4 will be reported for each arm. The primary analysis will be based on the evaluation of the least square estimate for the treatment arm effect which represents placebo-adjusted effect in lorundrostat treatment periods. Prior to the main estimation, a general linear model with effects of sequence, subject (sequence), period and treatment will be fitted to evaluate the existence of possible carryover/sequence effect.

Statistical approaches for the exploratory endpoints will be described in the statistical analysis plan (SAP).

AEs will be tabulated by Medical Dictionary for Regulatory Activities (MedDRA) system organ class (SOC), preferred term (PT), as well as by severity, causality, and time to occurrence.

Figure 1 Study Flow

* Either study provided commercially available dapagliflozin 10mg QD or continue regularly prescribed SGLT2i

**End of Study: [REDACTED] OLE will attend a 2week End of Study Safety Followup visit.

Abbreviations: OLE, [REDACTED]; QD [REDACTED] LT2 [REDACTED] 2 [REDACTED]

Table 1: Schedule of Assessments

Study Period	Screening ¹	Run-in	Randomization ²	Treatment Period 1 (4 weeks)		Wash Out (4 weeks)	Treatment Period 2 (4 weeks)		EoS ³	
Weeks ⁵	-4	-2	0	2	4	8	10	EOT 12	14	
Study Visit#	1	2	3	4	5	6	7	8	9	
Informed Consent ⁶	X									
Randomization			X							
Demographics	X									
Medical history	X									
Eligibility confirmed	X		X							
Concomitant medications	X	X	X	X	X	X	X	X	X	
Physical exam, body weight, height, waist and hip circumference ⁷	X		X	X	X	X	X	X	X	
Vital signs	X	X	X	X	X	X	X	X	X	
AOBP, seated and standing	X		X	X	X	X	X	X	X	
12-lead ECG	X		X						X	
Serum chemistry (including eGFR, excluding potassium) central lab	X		X	X	X	X	X	X	X	
Cystatin-C (central lab)	X		X	X	X	X	X	X	X	
Serum potassium (local lab)	X		X ⁸	X	X	X	X	X	X	
HbA _{1C} (central lab)	X				X			X	X	
Hematology (central lab)			X		X			X	X	
Urinalysis, spot urine (central lab)	X				X			X	X	
Dispense kit for first morning urine void	X	X		X			X			
Subject collects first morning urine void, midstream ⁹	X		X		X			X		
Dispense kit, for 24-hour urine ¹⁰	X	X		X	X		X			
Subject collects 24-hour urine ¹¹		X	X		X	X		X		
Pregnancy test ¹²	X		X			X		X	X	
Adverse events ¹³	X	X	X	X	X	X	X	X	X	
Study drug dispensed		X ¹⁴	X		X	X				
In-clinic dosing			X	X	X	X	X	X		
Study drug compliance			X	X	X	X	X	X	X	
Biomarkers (central lab) ¹⁵			X		X	X		X	X	
Morning serum cortisol ¹⁶	X			X	X		X	X		
PK (sampling) ¹⁷				X	X		X	X		
ACTH stimulation test ¹⁸										

Abbreviations: ACTH, adrenocorticotrophic hormone; AE, adverse event; AESIs, adverse events of special interest; AOBP, automated office blood pressure; ECG, electrocardiogram; eGFR, estimated glomerular filtration rate; EoS, End of study; EOT, end of treatment; HbA_{1C}, glycosylated hemoglobin; PK, pharmacokinetics; SAE, serious adverse event; SGLT2i, sodium-glucose cotransporter-2 inhibitor; ██████████.

1 Screening will be 2 weeks. However, if required, the screening window may be extended to 4 weeks without approval from the Medical Monitor.

2 Only subjects who continue to meet all eligibility criteria will be randomized.

3 Visit for subjects not participating in the open label extension study only. Study visit window is \pm 5 days.

4 Assessments performed during an unscheduled visit will be done on an as needed basis.

5 Study visit windows (double blind period and run-in) are \pm 3 days.

6 Written informed consent must be obtained prior to conducting any study procedures.

7 At the Screening Visit a physical examination will be performed and should include an evaluation of the cardiovascular, dermatologic, musculoskeletal, respiratory, gastrointestinal, and neurologic systems. Height will be measured at Screening only. At other visits, a limited, symptom-directed physical examination should be performed. Any abnormality identified should be recorded either as medical history or AE accordingly.

8 Serum potassium must be collected 3 days prior to Randomization and values must be reviewed by the Investigator for Randomization eligibility.

9 During Screening, one first morning urine void to be brought in, in the first week after Screening to determine eligibility. An unscheduled visit during Screening period for subjects to return first morning void must take place a minimum of 7 days prior to the Run-in visit so that the result is available for eligibility review. The sample needs to be 200-5000 mg/g inclusive to meet eligibility criteria. Samples will be assessed for albumin, protein, and creatinine.

10 Subjects will be given a 24-hour urine collection kit to take home at preceding visits. An aliquot of urine will be retained for future biomarker assessments.

11 Subjects must start urine collection on Day-1 and return the collected 24-hour urine on Week 0 Randomization visit. 24-hour urine samples will be utilized for assessment of albumin, protein, creatinine, sodium, potassium, cortisol, and aldosterone. An aliquot of urine will be retained for future assessments.

12 Women of childbearing potential only. A sample for serum pregnancy test will be collected at Screening. Follicle stimulating hormone must be used to confirm postmenopausal status in all postmenopausal women at Screening. Urine pregnancy tests will be done at other visits. If urine pregnancy test is positive, a serum pregnancy test will be collected to confirm results at the local lab.

13 All AEs and SAEs will be collected from signing of informed consent form until the subject has completed the EoS visit or transitioned to the open label extension study. All AESIs will be collected upon initiation of treatment until the subject has completed the EoS visit or transitioned to the open label extension study.

14 Only for SGLT2i naïve patient or patient switching to sponsor provided SGLT2i.

15 An aliquot of serum will be retained for future biomarker assessments. A sample of whole blood will be collected at Randomization and retained for future proteomic and genomic assessments. A mid-stream urine sample will also be collected for future biomarker analyses. Blood and urine samples will be processed and stored as described in the laboratory manual.

16 Blood draw for cortisol assessment should occur as close to 8 AM as possible on the morning of the study visit.

17 Subjects should have a blood sample drawn just prior to dosing and another blood sample taken 1-2 hrs. post-dose.

18 ACTH (Cosyntropin) stimulation testing to be performed at unscheduled visits if clinically indicated by signs, including serum cortisol below 3 µg/dL, or below 10 µg/dL accompanied by symptoms of hypocortisolism.

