3.2.3. Safety Endpoints

- Incidence and severity of AEs
- Clinically significant changes in vital signs (body temperature, heart rate, and respiratory rate), physical examination and ECG parameters
- Clinically significant changes in clinical laboratory assessments (hematology, chemistry, and urinalysis)
- Incidence of AEs of Special Interest (AESI)
 - Modification of study drug dose due to hyperkalemia (e.g., dose reduction, dose hold, or permanent dose discontinuation)
 - Modification of study drug dose due to hyponatremia (e.g., dose reduction, dose hold, or permanent dose discontinuation)
 - Hypotension with symptoms (e.g., light-headedness, dizziness, presyncope, or syncope)
 - Severely elevated BP (AOBP SBP >180 mmHg or AOBP DBP >110 mmHg)
 - Modification of study drug dose due to hypercortisolism (morning serum cortisol >35 µg/dL, confirmed by 24-hour urinary free cortisol)
 - Discontinuation of study drug due to hypocortisolism confirmed by ACTH stimulation test
 - Overdose of study drug

- Modification of study drug dose due to reduction in kidney function (e.g., dose reduction, dose hold, or permanent dose discontinuation)

■

■

■

■

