5.1 Inclusion Criteria

Subjects eligible for inclusion in this study must meet **all** the following criteria:

1. Written informed consent, obtained before any study-related assessment is performed
2. At least 18 years of age at the time of signing the informed consent form (ICF)
3. At Screening, UACR of 200-5000 mg/g, inclusive, in first morning urine void
4. At Screening, eGFR of ≥ 30 mL/min/1.73 m²
5. At Screening, AOBP SBP of 135-180 mmHg, inclusive
6. At Randomization, AOBP SBP of 135-180 mmHg, inclusive
7. On a stable treatment with an ACEi or ARB for at least 4 weeks prior to Screening
8. At Screening, serum cortisol (morning measurement, blood draw as close to 8 AM as possible between 3 and 22 µg/dL, inclusive)
9. At Screening, body mass index (BMI) of ≥ 18 kg/m²
10. Fertile male subjects and female subjects of childbearing potential must agree to use an acceptable method of contraception ([Appendix 12.4](#)) from the Screening Visit to 28 days after the last dose of study drug in each study part
11. Willing and able to comply with the study instructions and attend all scheduled study visits, and are capable of providing informed consent

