20. Use of epithelial sodium channel (ENaC) inhibitors or MRAs, including, but not limited to amiloride, triamterene, spironolactone, eplerenone, finerenone, from 4 weeks prior to the Screening Visit and during study participation. With the exception of MRAs in primary aldosteronism.
21. Medical history of kidney disease related to autoimmune diseases (lupus, anti-neutrophil cytoplasmic antibody [ANCA] vasculitis), multiple myeloma or other known paraproteins, infiltrative diseases of the kidney, obstructive nephropathy, cystic kidney diseases, and renal transplantation
22. Medical history of advanced liver disease, including cirrhosis
23. Medical history of active autoimmune disease or recent (within 30 days) or anticipated need for immunosuppressive therapy
24. Subjects with a medical history of urosepsis and pyelonephritis, lower limb amputation, genital mycotic infections, necrotizing fasciitis of the perineum (Fournier's Gangrene)
25. History of heart failure, myocardial infarction, stroke, or transient ischemic attack within 6 months prior to Screening. Heart failure of New York Heart Association (NYHA) Class II or more requires approval by the Medical Monitor

26. Diabetes mellitus with a glycosylated hemoglobin (HbA_{1c}) >10% (>86 mmol/mol) at Screening
27. Planned major surgery requiring hospitalization during the study period or performed within 4 weeks prior to the Screening Visit
28. History of malignant neoplasms within the 5 years prior to Screening except for known history of basal and squamous cell skin cancer and any carcinoma *in-situ*
29. Known or suspected abuse of illicit drugs or alcohol within 1 year prior to the Screening Visit
30. In the opinion of the PI, any other condition that will preclude participation in the study

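### Entry criteria cap systolic AOBP at 180 mmHg but set no diastolic limit; a DBP ceiling of 110 mmHg would be a minor, cheap safety improvement

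*Protocol*

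**What the plan says.** Inclusion criterion 5 reads "At Screening, AOBP SBP of 135-180 mmHg, inclusive" and criterion 6 reads "At Randomization, AOBP SBP of 135-180 mmHg, inclusive". Both appear in the synopsis and in Protocol Section 5.1.

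The only other numeric blood-pressure limits at entry are in exclusion 19b, for subjects with primary hyperaldosteronism: "They should have <20 mmHg increase in AOBP SBP, and AOBP SBP <150 mmHg at Randomization". They are also systolic. Exclusion 14 concerns past hospitalization for urgent or emergent hypertension and names no pressure.

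The safety endpoints list, as an adverse event of special interest (AESI), "Severely elevated BP (AOBP SBP >180 mmHg or AOBP DBP >110 mmHg"). The synopsis and SAP Sections 3.3 and 6.6.2.3 use the same two thresholds.

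Two routes could keep out a subject with a high DBP, and both depend on judgement:

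- The discretionary exclusion (synopsis no. 31; Section 5.2 no. 30): "In the opinion of the PI, any other condition that will preclude participation in the study".
- Exclusion 4, which covers anticipated use of a prohibited medication under Section 6.9. That section lets antihypertensives beyond those prescribed at Screening be used with investigator approval and a report to the Medical Monitor. It ends by sending eligibility questions to the Medical Monitor.

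Table 1 schedules "AOBP, seated and standing" at Screening and at Randomization, and Section 8.2.3 has DBP recorded with SBP.

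**The concern.** The systolic ceiling of 180 mmHg has the effect of keeping out anyone who already exceeds the systolic threshold of the AESI. Nothing does the same for the diastolic threshold, which is sufficient on its own, and the documents give no reason for the difference.

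What is at stake is individual safety and uniform eligibility:

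- Each subject takes placebo for 8 consecutive weeks: Weeks 0 to 8 in sequence PL and Weeks 4 to 12 in sequence LP. Table 1 schedules no AOBP between Weeks 4 and 8.
- Whether a DBP above 110 mmHg bars entry is left to 30–40 sites, although the protocol sets numeric entry limits for SBP, potassium, sodium, cortisol and HbA1c.
- Section 8.4.7.4 has sites adjust the antihypertensive regimen for severely elevated pressure. Its thresholds are blacked out. If they match the AESI definition, such a subject would need a change at entry, although the design has subjects continue their background therapy through both treatment periods and the washout. The footnote to SAP Table 5 says such changes are not intercurrent events, so the later readings stay in the primary analysis.

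**Working it through.** **Step 1: the text.** The plan has no figure to reproduce here. Both eligibility lists (synopsis; Sections 5.1 and 5.2) are unredacted, so the missing limit is not a redaction effect.

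| Threshold in the AESI | Matching numeric entry limit |
|---|---|
| SBP >180 mmHg | Yes: SBP ≤180 mmHg, criteria 5 and 6 |
| DBP >110 mmHg | None |

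Test case: 165/114 mmHg at both visits. Since 135 ≤ 165 ≤ 180, criteria 5 and 6 are met. No numeric criterion is failed, and 114 > 110.

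**Step 2: how many subjects.** The documents give no DBP data, so every input here is an assumption. Before selection:

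- SBP: mean 140, SD 16 mmHg, between-visit correlation 0.6.
- DBP: mean 78 or 82, SD 10 or 12 mmHg.
- SBP–DBP correlation ρ: 0.3 or 0.6 at the same visit, and 0.6ρ across visits.

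I simulated SBP at Screening, SBP at Randomization and DBP at Randomization as trivariate normal, with 8,000,000 draws per scenario. I kept draws with both SBPs in 135–180 mmHg: 47% were kept, with mean SBP 150.8 mmHg and mean DBP 80–87 mmHg. With p = P(DBP >110) among those kept, the expected count is 60p and the chance of at least one is 1 − (1 − p)^60.

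| DBP mean/SD | ρ | p | Expected in 60 | At least one |
|---|---|---|---|---|
| 78/10 | 0.3 | 0.10% | 0.06 | 6% |
| 78/10 | 0.6 | 0.09% | 0.05 | 5% |
| 78/12 | 0.3 | 0.57% | 0.34 | 29% |
| 78/12 | 0.6 | 0.59% | 0.35 | 30% |
| 82/10 | 0.3 | 0.38% | 0.23 | 20% |
| 82/10 | 0.6 | 0.38% | 0.23 | 20% |
| 82/12 | 0.3 | 1.42% | 0.85 | 58% |
| 82/12 | 0.6 | 1.55% | 0.93 | 61% |

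Even in the last row, the chance of none or one is (1 − p)^60 + 60p(1 − p)^59 = 0.39 + 0.37 = 0.76.

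**Step 3: effect on the primary estimate.** As an approximation to the planned mixed model, take the simple 2×2 estimate: half the difference between the two sequences' mean period differences. A change d in one of 30 subjects in Period 1 moves it by d/(2 × 30). For an assumed d of 5–10 mmHg from a regimen change:

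- 5/60 = 0.083 mmHg
- 10/60 = 0.167 mmHg

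The shift is smaller if the change persists into Period 2.

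The standard error implied by 85% power at 5.5 mmHg with one-sided alpha 0.05 is 5.5/(1.645 + 1.036) = 2.05 mmHg. The shift is therefore 0.083/2.05 = 4% to 0.167/2.05 = 8% of one standard error.

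**The case against.** The strongest reply is that this borrows a reporting trigger as an entry standard. The >180/>110 definition appears only as an AESI. Section 8.4.7 requires reporting of treatment-emergent AESIs, and Section 8.4.1 collects them from Randomization. Nothing says the 180 mmHg ceiling was chosen to match it; 135–180 mmHg is also simply an entry range on the primary endpoint variable. This stands. A reader might infer that the criteria contradict the safety definition, or that such a subject enters with an AESI already counted. The documents support neither: no statement conflicts with another, and a DBP above 110 mmHg before the first dose may not count as treatment-emergent.

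A reader might also infer that the discretionary exclusion is the only safeguard at entry. It is not. Exclusion 4 with Section 6.9 is a second route with Medical Monitor input, though not an automatic bar, because added antihypertensives can be approved.

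Harm after entry is limited. Section 8.4.7.4 covers diastolic as well as systolic elevation, calls for regimen adjustment and recommends doxazosin 1 mg if more is needed. The dose-modification text before Section 6.8 requires repeat AOBP and allows interruption of study drug. A DMC reviews unblinded safety data. Background therapy continues, so assignment to placebo withdraws no antihypertensive. The investigator can see DBP at Screening and Week 0.

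Finally, the counts rest on chosen inputs, span about 18-fold (0.05 to 0.93), and give no credit for anyone acting on a high reading. The upper end is a worst case within those inputs.

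What remains is narrower: each entry safeguard depends on individual judgement, and the later ones manage the subject after randomization without settling eligibility.

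**Conclusion.** The omission is certain on the text: no numeric criterion limits DBP, so a subject above 110 mmHg can be randomized unless someone uses judgement to prevent it. It is a minor point of patient safety and uniform eligibility, worth closing because doing so is cheap. It is not an error that makes the plan unworkable.

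The size is much less certain. Under the assumed distributions, probably none or one of 60 subjects is affected. The need for a regimen change at entry is conditional on the redacted Section 8.4.7.4 thresholds matching the AESI definition. A reader might infer from the intercurrent-event footnote that the primary result is at risk; a shift of 4–8% of a standard error from one such subject does not support that.

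**What to change.** Add *and AOBP DBP ≤110 mmHg* to inclusion criteria 5 and 6 (Screening and Randomization), in the synopsis and in Section 5.1. This uses the sponsor's own threshold and a measurement already taken at both visits. No SAP change is needed.

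The cost is a few words in two criteria, in two places, and a few extra screen failures at most. Repeat AOBP at entry is allowed only for technical failure, so a borderline diastolic reading would send the subject to rescreening. After approval, the change is an amendment requiring IRB/IEC approval (Section 10.3).

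SAP Section 1.2 states that the study was completed under Amendment 3. The edit is therefore useful only if made before enrollment or carried into a later protocol.
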